6.10.1. Terms and Definitions

6.10.1.1. Sample ADA Status

- Baseline ADA-positive sample: ADA is detected in the last sample before initiation of treatment
- Baseline ADA-negative sample: ADA is not detected in the last sample before initiation of treatment.
- **Treatment-emergent ADA-Positive**: Meets definition of treatment-induced or treatment-boosted ADA:
 - Treatment-induced ADA-Positive: a post-treatment positive ADA is detected in a subject for whom pre-treatment ADA assessment is either negative or not assessable
 - Treatment-boosted ADA-Positive: pre-existing ADA was boosted to a higher level following study treatment, i.e. pre-treatment positive ADA titer was boosted by at least 2 dilution steps (4-fold) following study treatment.
- **ADA-negative sample**: After initiation of treatment, ADA is not treatment-emergent ADA-positive.

Next, using the sample ADA status, the subject's ADA status is defined.

6.10.1.2. Subject ADA Status

- Baseline ADA-positive subject: A subject with a baseline ADA-positive sample.
- Baseline ADA-negative subject: A subject with a baseline ADA-negative sample.
- ADA-positive subject: An evaluable subject with at least one treatment-emergent ADA-positive sample at any time during the study.
- Neutralizing-positive: At least one treatment-emergent ADA-positive sample with neutralizing antibodies detected (if available).
- ADA-negative subject: An evaluable patient without a treatment-emergent ADA sample during the study.
- **ADA**-unknown: Patients without evaluable baseline and/or post-baseline ADA samples will be categorized as "ADA-unknown".

6.10.2. Statistical Analysis for Characterization of ADA Immune Response

6.10.2.1. Incidence of ADA

• Percentage of treatment-emergent ADA patients for the defined study period, where the denominator is the number of ADA evaluable patients in the respective treatment arm and/or subgroup.

Confidential Page 35 of 56

- Number (%) of subjects will be reported for the following parameters based on evaluable subjects:
 - Baseline ADA-positive
 - Treatment-emergent ADA-positive (Treatment-induced, Treatment-boosted)
 - Neutralizing Positive (if available)
 - ADA-negative
- **ADA prevalence**: Percentage of treatment-emergent ADA patients at any given timepoint, where the denominator is the number of ADA evaluable patients in the respective treatment arm and/or subgroup at that timepoint.
- A listing of all ADA assessments will be provided.
- Additionally, a separate listing of ADA assessments for all neutralizing antibody (NAb)-positive subjects will be provided (if available).

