6.2.4.2.2. Human Anti-Human Antibodies (HAHA)

Plasma samples will be collected for evaluation of human anti-human antibodies (HAHA) , in all subjects according to the SOA in Appendix 2. A specialty laboratory will measure HAHA titers using a validated assay.

Samples with positive HAHA results will be tested for neutralizing antibody (HAHA-NA) . The prevalence and duration of binding and neutralizing antibodies and the effect of these antibodies on the pharmacokinetics, pharmacodynamics markers, efficacy, and safety of pamrevlumab will be assessed.

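### SAP 6.10.2.1 defines ADA prevalence with treatment-emergent patients only, so it reports incidence by visit and leaves out persisting pre-existing antibody, binding or neutralizing

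*SAP*

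**What the plan says.** Protocol 6.2.4.2.2 has HAHA measured in all subjects and positive samples tested for neutralizing antibody. It then commits to assessing "The prevalence and duration of binding and neutralizing antibodies and the effect of these antibodies on the pharmacokinetics, pharmacodynamics markers, efficacy, and safety" of the drug. Protocol Appendix 2 includes a pre-dose Day 1 sample.

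The double-blind SAP turns this into definitions:

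- **Treatment-emergent (6.10.1.1).** Either induced (antibody after treatment where the pre-treatment sample was negative or not assessable) or boosted, meaning "pre-treatment positive ADA titer was boosted by at least 2 dilution steps (4-fold) following study treatment".
- **ADA-negative sample (6.10.1.1).** "After initiation of treatment, ADA is not treatment-emergent ADA-positive".
- **ADA-negative subject (6.10.1.2).** "An evaluable patient without a treatment-emergent ADA sample during the study".
- **Neutralizing-positive subject (6.10.1.2).** "At least one treatment-emergent ADA-positive sample with neutralizing antibodies detected".
- **Incidence (6.10.2.1).** "Percentage of treatment-emergent ADA patients for the defined study period, where the denominator is the number of ADA evaluable patients" in the arm or subgroup.
- **Prevalence (6.10.2.1).** "Percentage of treatment-emergent ADA patients at any given timepoint, where the denominator is the number of ADA evaluable patients" at that timepoint.

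ADA status then defines a possible FVC subgroup (6.7.1.4: positive, negative or unknown), the AE subgroups (6.8.1), and the PK, AE and primary-endpoint summaries (6.10.3). Titer kinetics (6.10.2.2) are restricted to ADA-positive subjects. SAP section 7, which lists changes from the protocol, does not mention immunogenicity.

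**The concern.** Incidence and prevalence share the same numerator and differ only in time frame. Prevalence would normally answer how many subjects carry detectable antibody at a given visit, whatever its origin. As defined, it cannot answer that. A subject who enters with antibody and keeps it at a similar titer is absent from the figure at every visit.

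Two consequences follow. A protocol commitment is narrowed without being declared as a change, for binding and neutralizing antibody alike. And in every summary by ADA status, a subject with persisting, unboosted antibody is grouped with subjects who have none. If pre-existing antibody acts on drug levels or reactions as newly formed antibody does, this pulls the contrast toward no difference.

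**Working it through.** The plan states no figure to reproduce for this point, so the check applies the definitions case by case and then illustrates the size.

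**Step 1: classify every case under SAP 6.10.1.**

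| Baseline sample | Post-dose sample | Antibody detected post-dose? | SAP label post-dose |
|---|---|---|---|
| Negative | Not detected | No | ADA-negative |
| Negative | Detected | Yes | Treatment-emergent (induced) |
| Positive | Not detected | No | ADA-negative |
| Positive | Detected, less than 4-fold rise | Yes | **ADA-negative** |
| Positive | Detected, at least 4-fold rise | Yes | Treatment-emergent (boosted) |

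Only one case has antibody detected after treatment and an ADA-negative label: baseline positive, still positive, not boosted. The threshold itself is coherent if dilution steps are two-fold, since 2² = 4.

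**Step 2: what the definition yields.** On Day 1, before dosing, no sample can be treatment-emergent, so prevalence is 0% whatever the baseline rate. At later visits:

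- SAP prevalence = treatment-emergent rate
- All-detected prevalence = treatment-emergent rate + (baseline-positive rate × share still detected without a 4-fold rise)

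**Step 3: size.** Inputs are about 170 subjects per arm (Protocol 3.4.1), all taken as evaluable, and assumed baseline-positive rates of 2%, 5% and 10%, because the documents give none.

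Upper bound, with 80% of baseline positives unboosted and all of them still detectable:

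- 170 × 0.02 × 0.8 = 2.7 subjects, a gap of 0.02 × 0.8 = 1.6 points
- 170 × 0.05 × 0.8 = 6.8 subjects, a gap of 4 points
- 170 × 0.10 × 0.8 = 13.6 subjects, a gap of 8 points

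If only half of the baseline positives remain detectable without a boost:

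- 170 × 0.02 × 0.5 = 1.7 subjects
- 170 × 0.05 × 0.5 = 4.25 subjects
- 170 × 0.10 × 0.5 = 8.5 subjects

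With an assumed treatment-emergent rate of 3%, SAP prevalence is 3.0% in every scenario. Counting all detected antibody gives 3 + 1.0 = 4.0%, 3 + 2.5 = 5.5% and 3 + 5.0 = 8.0% under the half-persisting assumption.

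**Step 4: effect on contrasts by ADA status.** With treatment-emergent incidence assumed at 2 to 5% (3 to 9 of 170), the ADA-negative group has about 161 to 167 subjects; take 164. The share of unboosted carriers in it is at most 2.7/164 = 1.7%, 6.8/164 = 4.1% or 13.6/164 = 8.3%. If carriers behaved exactly like ADA-positive subjects, the observed contrast would be (1 − share) times the true one, a relative shrinkage of about 2 to 8%.

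**The case against.** The strongest reply is that these subjects are recoverable. The 6.10.2.1 table has a baseline-positive row and splits treatment-emergent cases into induced and boosted. A boosted subject must be baseline-positive, so baseline-positive minus boosted gives the unboosted count. All ADA assessments are listed, and individual concentration plots carry antibody-response identifiers (6.10.3.1). This stands, but only for a whole-study total. The subtraction does not show how many unboosted subjects still have detectable antibody at a given visit. The separate listing for neutralizing-positive subjects would, under 6.10.1.2, omit baseline neutralizers with no treatment-emergent neutralizing sample.

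Second, Protocol 6.2.4.2.2 does not define prevalence, Protocol 8.5 leaves definitions to the SAP, and Protocol 3.2.4 and 8.3.6 speak of antibody formation. A treatment-emergent split is therefore defensible for incidence and for exploratory summaries. That also stands. It does not justify using the same numerator for a measure called prevalence when the protocol names prevalence without a restriction.

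Third, a reader might infer more than the text supports:

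- That every sample that is not treatment-emergent is called negative. Baseline samples keep their own positive and negative labels.
- That neutralizing antibody present at first dose is never counted. It is counted if a boosted sample is also neutralizing.
- That unboosted carriers could outnumber the ADA-positive group and so distort the comparison. They sit in the much larger ADA-negative group, where their share is a few percent, while the ADA-positive side has perhaps 3 to 9 subjects and its sampling error would dominate.

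**Conclusion.** The prevalence definition is wrong as written. It yields incidence by visit and falls short of the protocol commitment, for binding and for neutralizing antibody. This conclusion rests on the definitions alone.

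The size is unknown, because it depends on a baseline rate that the documents do not give. The figures of 3/7/14 subjects and 1.6/4/8 points are ceilings: they assume the 2/5/10% baseline rates, an 80% unboosted share, and antibody that stays detectable at every visit. Subjects whose antibody becomes undetectable are correctly negative, and prior pamrevlumab exposure is an exclusion criterion, so the true number may be small.

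It would go too far to say that the efficacy or safety conclusions are biased. The summaries by ADA status are descriptive or exploratory, the dilution is about 2 to 8% at most on these inputs, and neither the primary test nor the testing hierarchy uses ADA status. The OLE SAP inherits the definitions but plans no subgroup analysis by ADA status, so there the matter is limited to its ADA table.

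**What to change.** Amend SAP 6.10 before unblinding:

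1. In 6.10.2.1, define prevalence at a timepoint as subjects with any ADA-positive sample then, pre-existing or treatment-emergent, divided by subjects with an evaluable sample then. Keep incidence as treatment-emergent only.
2. Report neutralizing status for all ADA-positive samples, baseline included, alongside the treatment-emergent neutralizing count.
3. Add a row for baseline-positive, not boosted. In the PK, AE and FVC summaries by ADA status, either separate this group from ADA-negative or add a sensitivity summary that leaves it out.

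The cost is definition wording, one table row and a supplementary split. The protocol already provides for the samples and assays. The downside is one more small category, which may be nearly empty.

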6.10.2.2. ADA Titer Kinetics

All ADA-positive subjects will be included in the analysis.

- Summary statistics of subject-level ADA titers using the maximum titer value within an ADA-positive subject will be presented for baseline ADA-negative subjects and baseline ADA-positive subjects. The median, interquartile range, and range of the maximum titers will be reported. For ADA-positive subjects with a baseline ADA-positive sample, the median and interquartile range of the fold increase from baseline in titer (ratio of maximum post-baseline titer to baseline titer) will also be reported. Graphical presentation of the summary data may be provided using boxplots, as appropriate.
- For sample-level ADA titers, boxplots of ADA titers at each assessment time point will be provided, as appropriate, to demonstrate whether the ADA levels tend to change over time during the treatment, along with ADA incidence at each assessment time point.
- Spider plots may be considered to show the trend of ADA titer over time.

6.10.3. Clinical Implication of ADA Immune Response

6.10.3.1. PK

• Effect of ADA response on drug exposure will be explored by examining the drug exposures using graphical plots or simple summary statistics of observed drug concentration levels by ADA status and sampling time. Corresponding numerical values of geometric mean, arithmetic mean, and standard deviation will be displayed under the figures.

Confidential Page 36 of 56

• A listing of drug concentrations will be provided. Time course of observed concentrations by study visit with identifiers for antibody response will be plotted for each subject separately.

6.10.3.2. Safety and Efficacy

• AEs and the primary efficacy endpoint will be summarized by ADA status (details in Section 6.7.1.4 and Section 6.8.1).

7. CHANGES FROM PROTOCOL

Based on the feedback from the Food and Drug Administration on a similar Phase 3 IPF study (protocol #: FGCL-3019-091), MMRM will be used as the primary analysis for FVC and RCM will be used as a sensitivity analysis. Supplemental and subgroup analyses for FVC will also use MMRM. The exploratory efficacy endpoint FVCpp will also be analyzed using MMRM.

In addition, with consideration of FDA recommendations for the FGCL-3019-091 study, the testing order was switched for the following secondary efficacy endpoints: "Time to the first occurrence of any component of clinical composite endpoint: acute IPF exacerbation, respiratory hospitalization, or death, whichever occurs first" and "Change in QLF volume from baseline at Week 48" (Table 3).

APPENDIX 1. HANDLING MISSING/INCOMPLETE DATES

Appendix 1.1 Missing/Incomplete AE Onset Date

The following imputation rules apply to the case where the start date is incomplete (i.e., partially missing) for adverse events. When the start date and the stop date are both incomplete for a patient, impute the start date first.

If the stop date is complete and the imputed start date is after the stop date, then the start date will be imputed using the stop date.

• Missing start time only

AEs with missing start times and which occur on a study-drug-dosing day will be considered as occurred after the study treatment administration on that day. No imputation on other missing time.

• Missing day and month

If the year is the same as the year of the first day on double-blind study treatment, then the day and month of the start date of the double-blind study treatment will be assigned to the missing fields.

If the year is different from the year of the first day on double-blind study treatment, then January 1 will be assigned to the missing fields.

• Missing month only

Treat day as missing and replace both month and day according to the above procedure.

• Missing day only

If the month and year are the same as the year and month of the first day of double-blind study treatment, then the start date of the double-blind study treatment will be assigned to the missing day.

If the month and year are different from the year and month of the first day of double-blind study treatment, then the first day of the month will be assigned to the missing day.

Missing year

No imputation.

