1. INTRODUCTION

This statistical analysis plan (SAP) is for the pre-specified reporting of study results for protocol FGCL-3019-095, amendment 2.0. This SAP documents the planned analyses only for the open-label extension (OLE) period. Specifications of tables, data listings, and figures (TLF) are contained in a separate document. A separate SAP details the statistical analyses and methods for the double-blind period of FGCL-3019-095.

In this document, only new definitions and rules will be described. Cross reference to the double-blind SAP will be made for definitions and rules that will follow the same methodology used for the double-blind period of the trial.

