5.3.5. Handling Dropouts and Missing Data

For handling of dropouts and missing data the same guidelines will be followed as described in SAP for the double-blind period. No imputations will be performed on post-death analysis visits.

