6.7.1. Adverse Events (AEs)

Follow the same guidelines as described in SAP for the double-blind period with additional PEY for OLE period on pamrevlumab will be provided.

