6.8.1. Adverse Events (AEs)

Adverse events will be coded using MedDRA.

A new or worsening AE occurring on or after the first dose of study drug and within 60 days after the last dose of study drug is defined as a treatment-emergent adverse event (TEAE). AEs that started after 1st dose in the OLE period will be excluded from the main study. Partially or incompletely missing AE start/stop date/time will be imputed (Appendix 1).

If more than one event occurs with the same system organ class (SOC) and preferred term (PT) for the same patient, the patient will be counted only once for that preferred term using the most severe and most related occurrence for the summarization by common terminology criteria for adverse events (CTCAE) severity grade and relationship to the study treatment. Relationship to study treatment will be imputed as "Related" for any TEAE with a missing value for relationship.

The cumulative incidence of the following AE categories including the number (%) of subjects will be produced:

- Summary of all AEs
- TEAEs by PT
- TEAEs by SOC and PT
- TEAEs by SOC, PT, and maximum severity
- TEAEs by SOC, PT, and investigator-determined relationship
- TEAEs with severity grade \geq 3 by SOC and PT
- TEAEs related to study treatment determined by the investigator by SOC and PT
- TEAEs with frequency \geq 5% of subjects in either treatment arm by SOC and PT

Confidential Page 31 of 56

- Non-serious TEAEs with frequency ≥ 5% of subjects in either treatment arm by SOC and PT (Note: this is required for ClinicalTrials.gov)
- TEAEs leading to discontinuation of study treatment by SOC and PT
- TEAEs leading to interruption of study treatment by SOC and PT
- Treatment-emergent serious AEs (TESAEs) by SOC and PT
- TESAEs by PT
- TESAEs by SOC, PT, and maximum severity
- TESAEs related to study treatment determined by the investigator by SOC and PT
- Fatal TESAEs (i.e., adverse events that have an outcome of death) by SOC and PT
- All-cause deaths

Listings of all adverse events, TESAEs, TEAEs leading to study treatment discontinuation, TEAEs leading to death, and all-cause deaths will be provided.

In addition, TEAEs and TESAEs will be presented by subgroups as described in Section 6.7.1.4 along with an additional subgroup assessment by concomitant steroid medication use.

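### The open-label extension inherits an AE onset-date rule anchored to the first double-blind dose, so some partly dated extension events are dated before the first extension dose

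*SAP*

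**What the plan says.** The OLE SAP, Section 1, explains that "In this document, only new definitions and rules will be described"; everything else follows the double-blind SAP. For adverse events, OLE SAP 6.7.1 reads: "Follow the same guidelines as described in SAP for the double-blind period with additional PEY for OLE period on pamrevlumab will be provided". The double-blind SAP, Section 6.8.1, sends incomplete AE dates to Appendix 1.

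Appendix 1.1 has these rules for an incomplete onset date:

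- Day and month missing, same year as the double-blind start: "then the day and month of the start date of the double-blind study treatment will be assigned to the missing fields".
- Day and month missing, different year: "then January 1 will be assigned to the missing fields".
- Day missing, same month and year as the double-blind start: the double-blind start date.
- Day missing, any other month: "then the first day of the month will be assigned to the missing day".
- Year missing: no imputation.

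The only safeguard concerns an imputed start that falls after a complete stop date. Nothing compares the imputed date with the first OLE dose.

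The periods are divided at that dose. Double-blind SAP 6.8.1 says "AEs that started after 1st dose in the OLE period will be excluded from the main study", and Protocol Appendix 6 assigns AEs before the first OLE dose to the main study. Double-blind TEAEs run to 60 days after the last dose and are tabulated by treatment actually received (SAP 5.2.3 and 6.8.1).

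**The concern.** Within the double-blind period the rule is cautious: an onset that could fall on either side of the first dose is placed on the dose date and counted as treatment-emergent. Carried unchanged into the OLE, it does the reverse. An onset that could fall on either side of the first OLE dose is placed on the 1st of the month or on 1 January, normally before that dose.

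The OLE SAP does re-anchor study day, most baselines, exposure and visit windows to the OLE (Sections 5.3.2, 5.3.3 and 6.5.1, Appendix 1). AE date imputation was left behind.

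The stated objective of the OLE is long-term safety. Its AE counts would lose events while its patient-exposure-years stay the same. For a subject who had placebo, an event on pamrevlumab could be tabulated under placebo. A back-dated event would also usually miss the rule in double-blind SAP 6.8.2 that ties infusion and anaphylactic reactions to the day of an infusion or the day after.

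**Working it through.** The plan gives no figure to reproduce, so the check applies Appendix 1.1 as written.

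**Inputs**

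- Week 48 dose on Day 337, 336 days after Day 1 (SAP Appendix 2).
- First OLE dose 21 ± 7 days after the Week 48 visit (Protocol Appendix 6), so typically 336 + 21 = 357 days after Day 1.
- Double-blind TEAE window: last dose + 60 days (SAP 6.8.1).
- OLE length 48 weeks = 336 days; 24 weeks (168 days) and 96 weeks (672 days) as an assumed range.
- Assumptions: onsets spread evenly over the OLE; first OLE dose equally likely on any day of the year.

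**1. Worked case.** Double-blind Day 1 on 10 Mar 2021, Week 48 dose on 9 Feb 2022, first OLE dose on 2 Mar 2022.

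| True onset | Missing | Imputed onset | Result |
|---|---|---|---|
| 20 Mar 2022 | day | 1 Mar 2022 | before OLE; 20 days after last double-blind dose, so a double-blind TEAE |
| 20 Apr 2022 | day | 1 Apr 2022 | stays in OLE |
| 20 Aug 2022 | day and month | 1 Jan 2022 | before OLE; a double-blind TEAE |
| 10 Feb 2023 | day and month | 1 Jan 2023 | stays in OLE |

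**2. Share moved, day missing.** If the first OLE dose is on day j of an M-day month, onsets on the remaining M − j + 1 days move, except when j = 1. Summed over j, that is M(M − 1)/2 per month. Over a 365-day year: 7 × 465 + 4 × 435 + 378 = 5,373. Average: 5,373/365 = 14.7 days of onsets. As a share of the OLE: 14.7/168 = 8.8%, **14.7/336 = 4.4%**, 14.7/672 = 2.2%.

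**3. Share moved, day and month missing.** The days left in the calendar year, capped at the OLE length L, give the sum over m = 1 to 364 of min(m, L).

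- L = 336: 336 × 337/2 + 28 × 336 = 66,024; /365 = 180.9 days; **/336 = 54%**.
- L = 168: 168 × 169/2 + 196 × 168 = 47,124; /365 = 129.1 days; /168 = 77%.
- L = 672: 364 × 365/2 = 66,430; /365 = 182 days; /672 = 27%.

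In the rare case where the double-blind start is in the same year, the imputed date is that start, which is also before the OLE.

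A calendar enumeration agrees. It took every double-blind start over three years, the Week 48 dose ± 7 days, and a first OLE dose 14, 21 or 28 days later. Daily onsets over 48 weeks gave 4.4% and 53.9%; onsets sampled every third day gave 4.7% and 54.2%.

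**4. Do moved events become double-blind TEAEs?** If the last dose was at Week 48, a moved date is at most 28 − 1 = 27 days after it, so all moved events are inside 60 days. OLE entry does not require full dosing, however (OLE SAP 3.1). With the first OLE dose at 357 days, moved day-missing dates lie between 327 and 356 days after Day 1. The window closes at 7 × (week of last dose) + 60:

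| Last double-blind dose | Window closes (days after Day 1) | Day missing: share in window | Day and month missing: share in window |
|---|---|---|---|
| Week 42 | 354 | 87% | 99% |
| Week 39 | 333 | 5% | 88% |
| Week 36 | 312 | 0% | 78% |

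The shares come from the daily enumeration. Moved events outside the window are in neither period's TEAE count.

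**5. After re-anchoring.** Taking the later of the first OLE dose date and the Appendix 1.1 date leaves none before the first OLE dose. The two moved events in step 1 would both be dated 2 Mar 2022.

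**The case against.** Several points against this are sound.

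- **Scope.** A reader might infer that partly dated OLE events in general are moved. They are not: only dates in the month (day missing) or year (day and month missing) of the first OLE dose move. Over 48 weeks about 95% of day-missing events stay.
- **Frequency.** OLE visits are every three weeks, staff ask about events since the previous visit, and onset date is a required field (Protocol 7.3.2). Incomplete data are queried (Protocol 11.3). A year-only onset should be rare, yet it produces the largest percentage.
- **Infusion reactions.** These are the best-dated events. Subjects are queried before and after each infusion and observed afterwards (Protocol 5.1.6), and a suspected reaction calls for timed blood samples.
- **Randomised comparison.** A reader might infer that the rule tilts it in favour of pamrevlumab. The documents do not support that. Events from ex-pamrevlumab subjects move into the pamrevlumab arm by the same rule, and the net effect depends on a difference between groups that is not given.
- **Database lock.** The OLE has its own lock (OLE SAP 6.2). An event entered after the double-blind lock would only be lost from the OLE tables. The documents do not say how many that would be.
- **Route of inheritance.** OLE SAP 5.3.5 says "For handling of dropouts and missing data the same guidelines will be followed as described in SAP for the double-blind period", but the matching double-blind section (5.3.5) does not mention date imputation. The inheritance rests on OLE SAP 6.7.1 and double-blind SAP 6.8.1.

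These points limit the size and consequences. They do not remove the defect: the inherited rule, followed literally, gives a wrong date, and nothing in either SAP overrides it.

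**Conclusion.** The point holds in limited form. It is a stated rule that misplaces certain events, not merely an omitted detail. The loss from the OLE tables runs in one direction; the effect on the randomised safety tables does not have a known direction. Attribution to placebo requires three things together: an ex-placebo subject, an imputed date within 60 days of the last double-blind dose, and a record present in the double-blind database.

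The shares of about 4.4% (day missing) and 54% (day and month missing) rest on even onsets over 48 weeks and would change with a different onset pattern or OLE length. Absolute counts cannot be given, are probably small, and fall in a phase that is only summarised descriptively. The correction is worth making because it is cheap and concerns the safety objective of the OLE.

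**What to change.** Add to the OLE SAP: for AEs first recorded on or after the first OLE dose, and not documented as starting earlier, a partial onset date whose known month and year (or year alone) match those of the first OLE dose is imputed as the later of the first OLE dose date and the Appendix 1.1 date. A complete stop date before that dose, or another record such as the pre-infusion query on that day, counts as documentation of earlier onset.

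Use the same period assignment in the double-blind tables. Leave events recorded before the first OLE dose under the existing rule. Moving every matching partial date would push genuine double-blind events out of the randomised tables. Apply the same anchor to concomitant medication start dates, which Appendix 1.3 ties to the same rule.

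The cost is a sentence or two in each SAP and a small change to the derivation, which needs the date or visit at which the event was first recorded. The downside is that a few events with true onset between the last double-blind visit and the first OLE dose may be counted in the OLE.
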